5. RANDOMIZATION, BLINDING, AND REPLACEMENT OF PATIENTS

This is an open-label study with the identity of the treatment known to the patients, Investigators, and Sponsor; therefore, no randomization or blinding procedures will be performed.

All patients will receive SQ3370 treatment according to the expansion group in which they are enrolled. Patients will be enrolled from all participating centers if at all possible.

Patients who are lost to follow-up or withdraw consent for study participation prior to administration of study drug may be replaced, at sponsor's discretion.

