2.2. PHASE 2A EXPANSION GROUPS

2.2.1. Objectives

2.2.1.1. Primary Objectives

- Further investigate the safety and tolerability profile of SQ3370 in anthracycline naïve patients with:
 - Group 1: Neo-adjuvant treatment of patients with STS of the extremity who are ineligible for primary surgical resection and under consideration for possible/probable amputation, with predefined anthracycline sensitive tumors.
 - Group 2: Patients with unresectable, locally advanced or metastatic STS, with predefined anthracycline sensitive tumors and compare safety and tolerability of the RP2D in two infusion schedules of SQP33 (3-day vs 5-day).
 - Group 3:
 - 3a) Patients with relapsed or metastatic squamous-cell head and neck cancer

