Compare safety and tolerability of the RP2D in two infusion schedules of SQP33 (3-day vs 5-day) in locally advanced, unresectable, STS who are anthracycline naïve and with defined anthracycline sensitive (expected historical ORR ~20%) histologies angiosarcomas, leiomyosarcoma, liposarcoma, synovial sarcoma, adult fibrosarcoma, and undifferentiated pleomorphic sarcoma.

Each treatment group will maintain the total dose of SQP33 per cycle constant and compare 2 different infusion schedules, a 3-day vs a 5-day schedule. The study will be guided by the Continuous Reassessment Method (CRM) design. The CRM model provides an indication of whether to alter the RP2D regimen (3-day dosing per 21-day cycle vs. 5-day dosing per 21-day cycle) based on a comparison of toxicity and efficacy data collected from participants enrolled. The participants will receive SQP33 at the RP2D administered IV as a 3-day dosing regimen per 21-day cycle or as a 5-day dosing regimen per 21-day cycle.

A toxicity rate at or above 15% for myelosuppression (Grade ≥ 3) related treatment emergent adverse events (TEAEs) (anemia and febrile neutropenia) would be considered unsafe for the cohort, and enrollment would stop. If the 3-day infusion is not well tolerated that group will close, the study will continue with the RP2D and 5-day schedule with the initial adaptive design phase.

Safety Monitoring

All available safety tolerability data will be presented and discussed at the SRC. The maximum inefficacy and minimum efficacy rates are based on historical ORR, with <20% ORR being undesirable, and >35% ORR being desirable. Up to 11 participants per arm will be enrolled. After approximately half (n=6 per arm) of participants in Expansion Group 2 have been enrolled and observed for at least 2 cycles or approximately 6-weeks and have had at least one post-baseline tumor assessment, an evaluation of all available data (safety, efficacy, and PK from both the Expansion and Dose Escalation parts of the study) will be performed by the SRC.

Group 3a: Head and Neck

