8.4.2.2. Secondary Endpoints

The endpoints below will be assessed by the Investigators. Time to event variables will be estimated using K-M methodology. Medians using the log-log transformation will be computed. Binary variables will be summarized by binomial response rates and their corresponding two-sided 95% exact CI. Quantitative variables will be summarized using the mean, median, minimum, and maximum values, and standard deviation. Categorical variables will be summarized using tables presenting counts and percentages for each category. Further explanation, description, and landmark analyses (e.g., at 12, 24 months) will be provided in the statistical analysis plan finalized before the first database lock.

- ORR is defined as the number and percentage of participants with a BOR of confirmed CR or PR. BOR is defined as the best response designation, recorded between the date of enrollment and the date of the initial objectively documented tumor progression per RECIST v1.1, date of death from any cause, or the date of subsequent therapy, whichever occurs first. For participants without documented progression or subsequent therapy, all available response designations will contribute to the BOR determination.
- DCR is defined as the proportion of participants whose BOR is CR or PR or SD among all randomized participants.

- DoR is defined as the time recorded between the date of enrollment and the date of the initial objectively documented tumor progression per RECIST v1.1, date of death from any cause, or the date of subsequent therapy, whichever occurs first. DoR will be evaluated for responders (i.e., participants with confirmed CR or PR) only.
- Histopathologic Response
- Surgical outcome amputation/limb salvage vs. planned
- Time to local-regional progression or distant progression is defined as the time between the date of enrollment and the date of local recurrence/relapse or distant progression.
- Local-recurrence-free survival is defined as time between the date of enrollment and the date of local recurrence/relapse or death from any cause, whichever occurs first.
- Distant-recurrence free survival is defined as time between the date of enrollment and the date of distant recurrence/relapse or death from any cause, whichever occurs first.
- Disease-free survival is defined as the time between the date of enrollment and the date of recurrence/relapse or death from any cause, whichever occurs first.

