Group 2 and the use of the CRM model provides an indication of whether to alter the RP2D regimen (3-day dosing per 21-day cycle vs. 5-day dosing per 21-day cycle) based on a comparison of toxicity and efficacy data collected from enrolled participants. The indicated population for the Group 2 participants is locally advanced or metastatic, unresectable, soft-tissue sarcoma of intermediate or high grade with evidence of disease progression and no prior anthracycline treatment, and thus the test statistics parameters for the CRM are based on historical toxicity and efficacy rates of said population (Table 10). The participants will receive SQP33 at the RP2D administered IV as a 3-day dosing regimen per 21-day cycle or as a 5-day dosing regimen per 21-day cycle. Participants may be replaced if they are enrolled into the study but do not receive (for reasons other than AEs/SAEs) the intended dose during Cycle 1. If Cycle 1 cannot be completed due to a COVID-19 infection, an additional patient may be enrolled in the group.

Continuous Reassessment Method Design Considerations

| Parameters | Continuous Reassessment Method (CRM) |
|--|---|
| Historical Rates of Toxicity ² | 
 • Anemia: Grade ≥ 3 [8%] • Febrile neutropenia Grade ≥ 3 [~20%] |
| Acceptable threshold for toxicity | Grade ≥ 3 Related Myelosuppression TEAEs* 
 • Anemia: Grade ≥ 3 <15% • Febrile neutropenia Grade ≥ 3 <15% |
| Maximum Inefficacy proportion ²⁻⁴ | 0.20 |
| Minimum Efficacy proportion ²⁻⁴ | 0.35 |
| Types I and II errors set at | 0.05 |
| Total number of pts per arm | 11 |
| Power | none |

*Myelosuppression TEAEs as per NCI-CTCAE v5.0- Anemia: Grade 3: Hgb <8.0 g/dL; <4.9 mmol/L; <80 g/L; transfusion indicated. Grade 4: Life-threatening consequences; urgent intervention indicated; Febrile Neutropenia: Grade 3-ANC <1000/mm³ with a single temperature of >38.3 degrees C (101 degrees F) or a sustained temperature of ≥ 38 degrees C (100.4 degrees F) for more than one hour. Grade 4: Life-threatening consequences; urgent intervention indicated.

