Test statistics parameters are based on historical toxicity and efficacy rates (Table 10). The acceptable threshold for toxicity is set at 15%, respectively. A toxicity rate at or above 15% for myelosuppression (Grade ≥ 3) related treatment emergent adverse events (TEAEs) (anemia and febrile neutropenia) would be considered unsafe for that group, and enrollment would stop. The maximum inefficacy and minimum efficacy rates are based on historical objective response rates (ORR), with <20% ORR being undesirable, and >35% ORR being desirable.

After approximately half (n=6 per arm) of participants in Group 2 have been enrolled and observed for at least 2 cycles or approximately 6-weeks and have had at least one post-baseline tumor assessment, an evaluation of all available data (safety, efficacy, and PK from both the Expansion and Dose Escalation) will be performed by the SRC, to determine whether to continue to enroll up to a total of 11 participants per arm or to stop enrollment of a group. See Section 7.1 (Interim Analysis) for more information regarding the Group 2 safety run-in.

Groups 1 and 3a will treat up to approximately 28 participants in Stage 1 and Group 2 will treat up to a total of 22 participants. For all Expansion Groups: Patients may be replaced if they are enrolled into the study but do not receive (for reasons other than AEs/SAEs) the intended dose during Cycle 1. If Cycle 1 cannot be completed due to a COVID-19 infection, an additional patient may be enrolled in the group.

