8. DATA PRESENTATION AND HANDLING

8.1 Table and Individual Patient Data Listing Considerations

Summary tables and listings will be prepared according to ICH Guideline E3 (as appropriate for a Phase 2A study).

In general, summary tables will be organized with respect to the Phase 2A expansion groups:

- Group 1: Extremity STS
- Group 2: Unresectable STS 3-Day Infusion
- Group 2: Unresectable STS 5-Day Infusion
- Group 3A: Head and Neck
- Total

Row entries in post text tables are made only if data exists for at least one patient (e.g., a row with all zeros will not appear). The only exception to this rule will apply to tables that summarize the study termination status of patients (e.g., reasons for not completing the study). In this case, zeros will appear for study termination reasons that no patient satisfied. The summary tables will clearly indicate the number of patients to which the data apply and unknown or not performed are distinguished from missing data.

Summary tables for any concomitant medications will be coded according to the World Health Organization (WHO) Drug dictionary September 2020 (or later). Adverse event preferred terms and body/organ systems and medical history conditions will be coded using the Medical Dictionary for Regulatory Activities (MedDRA®) dictionary Version 24.1 (or later).

Listings will also be sorted by expansion group (where applicable) and patient number. Listings will also include visit number, visit date/time and days relative to the initiation of study treatment.

In general, missing data will not be imputed unless otherwise specified. Any imputed or derived data will be flagged in the individual patient data listings. Imputed data will not be incorporated into any raw or primary datasets. These data will be retained in derived analysis datasets.

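### Phase 2a SAP section 5 rules out randomization only because the study is open-label, and no supplied text says how a Group 2 patient is placed on the 3-day or 5-day schedule, so the planned schedule comparison is open to selection bias

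*SAP*

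**What the plan says.** Section 5 of the Phase 2a SAP describes the study as open-label, with treatment known to all parties, and goes on: "therefore, no randomization or blinding procedures will be performed". It gives no other reason. Its only assignment rule is "All patients will receive SQ3370 treatment according to the expansion group in which they are enrolled". Both schedules sit inside Group 2. SAP 8.1 and 8.5 give each its own table column, such as "Group 2: Unresectable STS 3-Day Infusion", but do not say how a patient gets into one or the other.

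The comparison is planned. Protocol 2.2.1.1 and SAP 3.1 include in the primary objective, for Group 2, to "compare safety and tolerability of the RP2D in two infusion schedules of SQP33 (3-day vs 5-day"). The primary objective in the protocol synopsis omits it. The synopsis and protocol 2.2.2.2 also list it as a secondary endpoint for Group 2.

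It also has a stated use. Protocol 8.3 and SAP 4 say the CRM indicates whether to change the RP2D regimen from one schedule to the other, "based on a comparison of toxicity and efficacy data collected from enrolled participants".

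The DCR definition in protocol 8.4.2.2 takes its proportion "among all randomized participants". SAP 11.4 drops that phrase, and SAP 16 lists no changes from the protocol.

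**The concern.** The step from open-label to no randomization does not follow. Knowing the treatment rules out blinding; it leaves random allocation available. The Phase 1 SAP has the same sentence in its section 5. There it did no harm, because patients entered whichever dose cohort was open and no schedules were being compared. In Group 2 two schedules are compared.

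If patients reach a schedule by investigator, sponsor or patient preference, by site, or in sequence, the two arms may differ in prognosis or in tolerance of treatment. Protocol 4.2.2 admits six histologies, intermediate or high grade, and locally advanced or metastatic disease, so there is room for the mix to differ. SAP 9.2 plans no covariates and 9.3 no predefined subgroups, so nothing planned would adjust for it. At stake is whether the side-by-side comparison used to judge the regimen says something about the schedules or about the patients on them.

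**Working it through.** **1. Is there an allocation rule anywhere in the supplied text?**

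| Place | What it settles |
|---|---|
| SAP 5 | Treatment follows the expansion group; silent within Group 2 |
| Protocol synopsis, 3.1.4.1, 3.5.1, 8.3; SAP 2.3, 4 | Patients receive 3 or 5 days; no rule for which |
| Protocol 4.2.2 | One set of eligibility criteria for both schedules |
| Protocol 6.2 | No interactive voice or web response system |
| Protocol 6.3 | Eligibility and sponsor signature; silent on schedule |
| CRM text, protocol 3.5.1 and 8.3; SAP 4 | Guides sample size and gives an indication about the regimen; not said to assign patients |
| SAP 7.1 | 6 per arm at run-in, 11 per arm at the end; no method or order of assignment |

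No rule was found. The Pharmacy Manual, the sponsor's enrolment process and the expansion-group schema (protocol Figure 4) were not available to check.

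**2. The plan's own figures.** 2 × 6 = 12 at run-in and 2 × 11 = 22 in total, as stated. The CRM table gives power as none, so there is no power figure to reproduce.

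**3. Possible size of the bias (all inputs assumed).** Spurious gap = (difference between arms in the share of patients with a trait) × (effect of that trait on the event rate).
- Low: 0.20 × 0.10 = 0.02.
- High: 0.40 × 0.30 = 0.12.
- More extreme, shares of 20% and 80% and event rates of 10% and 50%: 0.60 × 0.40 = 0.24.

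This gives 2 to 12 points on moderate assumptions and 24 on strong ones. For scale, the plan's undesirable and desirable ORRs (20% and 35%) are 15 points apart.

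**4. Precision, with or without randomization.** Approximate 95% half-width for a difference = 1.96 × √(2p(1−p)/n).

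| Event rate p | n = 11 per arm | n = 6 per arm |
|---|---|---|
| 10% | 25 points | 34 points |
| 15% | 30 points | 40 points |
| 20% | 33 points | 45 points |

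Two-sided Fisher tests, counting up from zero events in one arm:
- 0/11 vs 4/11, p = 0.090; 0/11 vs 5/11, p = 0.035.
- 0/6 vs 4/6, p = 0.061; 0/6 vs 5/6, p = 0.015.

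**5. What randomization leaves to chance.** Assume 9 of 22 patients carry a trait and 11 go to each arm. By the hypergeometric distribution, a split of 6–3 or worse has probability 0.387. Randomization removes systematic selection; it does not guarantee balance.

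**The case against.** *The comparison is descriptive, has no power and no planned test, and any plausible bias sits inside its own confidence interval.* This stands, and it limits the point to interpretation and the regimen judgement; no formal error rate is affected. But a confidence interval displays imprecision and does not display selection.

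*Baseline imbalance would be visible.* Partly true. SAP 8.5 puts the two schedules in separate columns, and SAP 10.4 and 10.5 summarize demographics and baseline characteristics. Measured differences would show; unmeasured ones would not, and no adjustment is planned.

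*The CRM may be the allocation mechanism.* A reader might infer this because Group 2 is said to be guided by it. The text does not say that it assigns patients.

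*The rule may be in a document not supplied.* Possible. SAP 5 would still exclude randomization, on a reason that does not support it.

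A reader might also infer that the Group 2 stopping decisions are compromised. The documents do not support that. The 15% toxicity threshold is a fixed limit, the run-in response rule pools 12 patients, and the closure rule ("If the 3-day infusion is not well tolerated that group will close") concerns the 3-day arm alone. None is a contrast between arms. The SRC's continue-or-stop review also draws on "safety, efficacy, and PK from both the Expansion and Dose Escalation", so randomizing Group 2 would not turn that decision into a randomized comparison. PK is outside the point, because the daily doses differ by design.

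Nor does the DCR wording show that randomization was intended. The definition also serves Group 3a, which has one schedule, and reads as standard text. It is an inconsistency to tidy.

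**Conclusion.** The point holds in this form. SAP 5 excludes randomization for a reason that does not exclude it, and no supplied text gives a rule for entering the 3-day or 5-day schedule. The comparison is in the primary objective in the protocol body and the SAP, absent from the synopsis primary objective, and listed as a secondary endpoint. It informs whether the RP2D regimen is altered, and as planned it is open to selection bias.

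The direction and size of any bias are unknown; the 2 to 24 points above rest wholly on assumed inputs. A reader might conclude that patients are in fact being selected onto a schedule, or that the comparison is already biased. The documents do not show either, because they are silent on how assignment is done. The gain from randomizing is a comparison free of systematic selection, at unchanged and low precision. This is worth correcting, but it does not invalidate Group 2.

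**What to change.** In SAP 5 and protocol 3.3 and 6.3, state:
- While both schedules are open, Group 2 patients are assigned 1:1 from a concealed permuted-block list held by the study statistician and released at the sponsor's enrolment signature. Replacement patients take the next assignment. The study remains open-label.
- The CRM does not allocate patients; otherwise, reconcile the CRM text with this rule.
- The schedule comparison uses concurrently randomized patients and is descriptive, with confidence intervals. Other patients, such as those enrolled after one arm closes, stay in the arm summaries.

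For patients already enrolled without randomization, or if the sponsor keeps a non-random rule, state the rule, label the comparison non-randomized and draw no comparative conclusion. Reconcile the DCR wording in protocol 8.4.2.2 with SAP 5 and SAP 11.4, and record the outcome in SAP 16.

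Cost: a protocol and consent amendment with the required approvals, and loss of discretion over schedule. The randomized comparison would be smaller if enrolment has begun (its status is not given) or if one arm closes early. No extra patients, visits or response system are needed, because the sponsor already signs each enrolment. The Phase 2a SAP is still marked version 0.1, so its text can be edited. The fallback of stating the rule and labelling the comparison costs little more than the wording.

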6. DEFINITIONS OF PATIENT POPULATIONS TO BE ANALYZED

This study will have six analysis populations:

- Enrolled: All patients who sign consent.
- Treated / Full Analysis Set: All patients who receive at least 1 dose of SQL70 biopolymer and 1 dose of SQP33 protodrug.
- Efficacy Evaluable Analysis Set: All patients who receive at least 1 dose of SQL70 biopolymer and 1 dose of SQP33 protodrug and undergo at least 1 post baseline tumor evaluation.
- Safety Analysis Set: All patients who received at least 1 dose of SQL70 biopolymer and/or SQP33 protodrug.
- PK Analysis Set: All patients in the Safety Population who have the necessary Day 1 and on-study measurements to provide interpretable results for the specific parameters of interest.
- Biomarker Analysis Set: All patients with available biomarker data.

7. PLANNED ANALYSES

7.1 Interim Analysis

In Phase 2a, there will be two interim looks at the data:

- 1) run-in safety/tolerability and
- 2) Stage 1 of the Simon 2-stage design.

The SRC will utilize the same criteria to evaluate the safety and tolerability of all available safety data at the completion of timing for each group to determine the initial safety and monitor the groups throughout the study overall safety and tolerability.

Phase 2a Safety Evaluation Timing:

| Group | Run-in Evaluation N= (timing) | Simon Design: Stage 1 evaluation | Final Assessment |
|----------------------------|--|----------------------------------|------------------|
| 1: Extremity STS | N=6 (after cycle 1) | N=15 | N=46 |
| 2: STS unresectable | N=12 (6 per arm; after cycle 2) | N.A. | N=22 |
| 3a: Head and Neck | N.A. | N=13 | N=26 |

N.A.=Not Applicable

Group 3a: A run-in is not planned for the Head & Neck group (Group 3a) since they will be receiving the RP2D and schedule of SQ3370 without modifications.

Group 1: will receive SLQ70 in a volume of 20 mL with the RP2D of SQP33 and therefore the safety lead-in to this group is warranted. The SRC may, after the planned initial review of any group, within its purview recommend additional monitoring to the sponsor.

The above table also describes the Stage 1 analysis of efficacy/safety based on the Simon 2 stage design parameters.

For the Group 2 safety run-in, after approximately half (n=12 total or n=6 per arm) of patients in Expansion Group 2 have been enrolled and observed for at least 2 cycles (or approximately 6-weeks) and have had at least one post- baseline tumor assessment, an evaluation of all available data (safety, efficacy, pk) will be performed by the SRC to determine whether to continue to enroll up to Group 2 final total n=22 (n=11 per arm) or to stop enrollment.

With respect to efficacy, the minimum number of responders needed to continue to full enrollment of Group 2 will be based on the stage 1 parameters of the Simon 2-stage design. The maximum inefficacy and minimum efficacy rates are based on historical ORR and are <20% ORR being undesirable, and >35% ORR being desirable. Assuming 70% power and one-sided significance level of 0.10, with 12 Group 2 patients in the safety run-in, if ≤ 2 patients achieve either a CR or PR, then the study is considered futile and will be stopped. If ≥ 3 responders in 12 patients, then the Group 2 enrollment may continue to enroll to n=22.

